### 7. PROTOCOL ASSESSMENTS

# 7.1. TREATMENT, DAY 1

# 7.1.1. Medical management guidelines

Other interventions to optimize the care of subjects will be left to the discretion of the attending physician and investigator. These include surgical/nonsurgical debridement of devitalized tissue, removal of prosthetic material, incision and drainage, suture removal, percutaneous aspiration, packing, dressings, or irrigation with normal saline to remove superficial slough, excess exudate or visible debris. Standard of care therapy (such as daily superficial debridements and dressing changes) are allowed.

If a patient has an infusion reaction with oritavancin the infusion may be slowed or stopped. The patient should be treated as necessary. The infusion may be resumed at half the previous infusion rate with continued monitoring for signs or symptoms of a histamine infusion reaction.

If a patient is classified as a treatment failure by the investigator at any time, the patient may be administered alternative antibiotic therapy according to clinical judgment.

# 7.1.1.1. Gram-negative pathogen ABSSSI infections

Subjects enrolled and treated with oritavancin before culture results are available and found to have a Gram-negative pathogen may receive additional antibiotic therapy with gram-negative coverage.

#### 7.2. ASSESSMENT OF SAFETY

When blood draws and vital signs are done at the same timepoint, the following sequence should be followed: 1) vital sign assessment 2) blood draw for lab tests.

#### 7.2.1. Adverse Events

Subjects will be carefully monitored for adverse events by the investigator during the designated study period.

#### 7.2.2. Physical Examinations

A physical exam will include head, eyes, ears, nose, throat (HEENT), heart, lungs, abdomen, skin, and extremities. Body mass index (BMI) will be calculated based on height and weight collected at the Screening Visit.

#### 7.2.3. Vital signs

Vital signs (blood pressure, heart rate, respiratory rate and temperature) will be assessed at the designated time periods as indicated in the Schedule of Events.

Blood pressure and pulse must always be taken after the subject has been resting supine for 5 minutes.

## 7.2.4. Laboratory assessment

Specimens will be obtained at the designated time periods as indicated in the Schedule of Events. All clinical laboratory assessments will be performed by the site's local laboratory. Additional local laboratory testing may be performed at the discretion of the investigator. Any clinically significant lab findings that occur during the study should be followed to resolution per the Investigator/Sponsor's decision. If the PT/INR has not returned to baseline by Day 14, patient will be followed until PT/INR has returned to therapeutic baseline.

- Chemistry: Blood urea nitrogen, Serum creatinine, Total bilirubin, Direct bilirubin, Alkaline phosphatase, Aspartate aminotransferase, Alanine aminotransferase, Albumin, Total protein, Glucose, Calcium, Chloride, Sodium, Magnesium, Potassium, Uric acid, Lactate dehydrogenase, Bicarbonate, Phosphorus
- **Hematology:** Hemoglobin, Hematocrit, White blood cell count (with automated differential), Red blood cell count, Platelet count
- Coagulation Tests: PT/INR
- Urine Pregnancy Test
- Direct and Indirect Coombs test
- Immunoglobulin Panel Assays: Immunoglobulin M (IgM), Immunoglobulin G (IgG); Immunoglobulin E (IgE), Immunoglobulin A (IgA),
- Assay for oritavancin antibodies
- Plasma Storage Samples for Drug Dependent Antibody Ex Vivo Study

## 7.3. ASSESSMENT OF EFFICACY

#### **Definition of clinical response:**

#### Assessment of clinical cure at 48 to 72 hours:

A patient is classified as "success" if all of the following are met:

• Cessation of spread or reduction of the lesion defined as: Cessation of spread of the redness, edema, and/or induration or reduction in size (length, width,

and area) of the redness, edema, and/or induration such that the size of the lesion is less than or equal to the size at baseline

- Resolution (absence) of fever (temperature <37.7°C)
- No rescue antibiotic medication

A patient cannot be classified as a "success" at 48-72 hours (i.e., patient is a failure) if:

- Death (all-cause mortality) from the start of oritavancin administration
- Fever (one or more temperature readings of ≥37.7°C between 48 and 72 hours)
- Spread of lesion defined as an increase in size (length, width, or area) of the redness, edema, and/or induration such that the size of the lesion is greater than the size at baseline
- Administration of rescue antibacterial drug therapy or any non-trial antibacterial drug therapy for the treatment of ABSSSI prior to the 48-72 hours clinical cure evaluation
- Requires an additional unplanned surgical procedure after start of therapy as described below under: "A patient cannot be classified as clinical cure if"

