#### 5. TREATMENT OF SUBJECTS

# 5.1. STUDY MEDICATIONS

Each subject will receive a single 1200 mg IV dose of oritavancin. Oritavancin will be prepared by the study pharmacist/designee.

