# Investigator assessment of clinical cure:

At Day 7: Complete or nearly complete resolution of baseline signs and symptoms of the primary infection such that no further treatment with antibiotics is needed

A patient cannot be classified as clinical cure if:

- Patient did not fulfill criteria for clinical cure above
- Investigator assignment of failure any time prior to Day 7
- Patient dies (all-cause mortality) from the start of administration of oritavancin
- Incision and drainage after 48 hours of treatment that was unplanned prior to enrollment, with the exception of cellulitis where there is a conversion into an abscess or when an extension of the original incision is indicated
- Initiation of non-study antibacterial drugs for treatment of other infection unless antibiotic lacks efficacy in the treatment of ABSSSI
- Subjects who otherwise do not meet the definition of clinical cure (e.g., lost to follow-up; oritavancin discontinued secondary to adverse reaction)

A patient who is not classified as clinical cure will be classified as failure.

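### Protocol 7.3: an ABSSSI-active antibacterial started for a new infection bars cure at Day 7 but leaves success at 48-72 hours standing

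*Protocol*

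**What the plan says.** Clinical cure, judged by the investigator at 48-72 hours and at Day 7, is the secondary outcome (protocol 3.2; SAP 2.3.2). Protocol 7.3 gives each time point its own definition and its own list of events that rule it out.

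- **48-72 hours, success criteria.** Besides a lesion no larger than at baseline and no fever, the only antibiotic condition is "No rescue antibiotic medication".
- **48-72 hours, failure list.** The antibacterial item is "Administration of rescue antibacterial drug therapy or any non-trial antibacterial drug therapy for the treatment of ABSSSI", limited to use "prior to the 48-72 hours clinical cure evaluation". One further item points to the Day 7 list: "Requires an additional unplanned surgical procedure after start of therapy as described below under" the named Day 7 heading.
- **Day 7, failure list.** Cure is barred by, among other things, "Initiation of non-study antibacterial drugs for treatment of other infection unless antibiotic lacks efficacy in the treatment of ABSSSI".

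Exclusion 4d (protocol 4.3) keeps out patients who already have an infection at another site, apart from a secondary ABSSSI lesion. SAP section 7 says only that efficacy results will be listed, and it adds no classification rule.

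**The concern.** The two lists treat the same exposure differently. The early item looks at the purpose of the added drug: it counts if given as rescue or for the ABSSSI. The Day 7 item looks at activity: a drug given for something else still counts unless it does not work in ABSSSI. That is the sounder test of whether a good outcome can be credited to oritavancin, because an active drug acts on the skin lesion whatever the reason for prescribing it.

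At 48-72 hours, then, a favourable lesion response that may be partly due to another drug can be recorded as an oritavancin success. The study has no reference therapy, so no comparator would absorb the misattribution. What is at stake is the correct class of an individual patient and, where cure is summarised as the synopsis plans, the early proportion in a small group. The primary safety outcome is untouched.

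**Working it through.** No stated figure needs reproducing. The sample size rests on feasibility and judgment (protocol 10.1), with no test, power or threshold for clinical cure. The check is to run one case through both lists.

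**Test case.** After the oritavancin infusion starts and before the early evaluation, a patient starts an ABSSSI-active antibacterial for a newly arisen infection elsewhere. The lesion has not grown, there is no fever, nothing has been given for the ABSSSI, there has been no unplanned surgery, and the patient is alive.

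| Rule in 7.3 | 48-72 hours | Day 7 |
|---|---|---|
| Rescue drug, or drug given for the ABSSSI | Not triggered: the drug is for another infection | Not needed for this case |
| Active drug started for another infection | No such item | Triggered: cure barred |
| Unplanned surgery | Item borrowed from the Day 7 list; not triggered | Not triggered |
| Lesion growth, fever, death | Not triggered | No death; the other two are not separate Day 7 items |
| **Class** | **Success** | **Failure** |

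**Could another provision close the gap?**

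1. *The Day 7 list applies to both visits.* It sits under the Day 7 assessment, and the early assessment has its own list. That list refers to the Day 7 list for one item only, which indicates that the rest are not carried over.
2. *Rescue covers any added antibacterial.* The protocol does not define rescue. Its ordinary meaning is treatment because the treated infection is failing. If it already covered every added drug, the separate wording about non-trial drugs given for the ABSSSI would be unnecessary.
3. *Exclusion 4d prevents the case.* It acts at entry and does not reach an infection that arises after dosing.
4. *A later failure is carried back.* The only carry-over runs forward: "Investigator assignment of failure any time prior to Day 7" bars cure at Day 7. Nothing revises the early class.
5. *The SAP resolves it.* Section 7 plans listings only.

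**Size.** Inputs: planned group sizes of about 25 (warfarin) and 15 (non-warfarin), from protocol 4.1; summaries are by group (protocol 10.3). With x misclassified patients among n, the early proportion shifts by x/n. The documents give no value for x. It is assumed to be 0 or 1 per group, with all planned patients in the denominator.

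- Warfarin group: 0/25 = 0 to 1/25 = 4.0 percentage points.
- Non-warfarin group: 0/15 = 0 to 1/15 = 6.7 percentage points.

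**The case against.** The strongest reply is that two endpoints may properly have two rules. The early assessment asks whether spread and fever have stopped. Day 7 asks whether the infection has essentially resolved. A drug started after dosing has at most 72 hours to act before the first evaluation and about a week before the second, so a stricter later rule is plausible. The affected patient also fails at Day 7, and medications are recorded in the eCRF and listed by subject (protocol 5.2.1; SAP 6.3), so a careful reader would see a success followed by a failure and the reason for it. The path is narrow too: a new infection must arise, be diagnosed and be treated with an active drug within the window, in a patient who is afebrile with a stable lesion. Finally, the 4.0 and 6.7 point shifts reflect small groups; any single reclassification would produce them.

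Most of this stands as a limit on importance. It does not remove the inconsistency. The protocol gives no reason for the difference. A Day 7 failure does not correct the recorded early success, and early success is reported in its own right.

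A reader might go further and infer that the Day 7 list has a matching hole: that it does not name a drug given for the ABSSSI itself after the early evaluation and finished by Day 7, such as Gram-negative cover that also has Gram-positive activity. The documents do not support that as a finding. Day 7 cure requires resolution "such that no further treatment with antibiotics is needed", and protocol 5.1 states "Each subject will receive a single 1200 mg IV dose of oritavancin". Read together, these can mean that nothing beyond that one dose was needed, in which case cure is already barred. A hole appears only if the phrase looks forward from Day 7. An added Day 7 line would also fail patients for Gram-negative cover that protocol 5.2.2 and 7.1.1.1 expressly allow.

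**Conclusion.** The inconsistency is real and follows from the text of 7.3: an ABSSSI-active antibacterial started for a new infection between dosing and the early evaluation leaves an early success on record, although the plan's own Day 7 rule treats that exposure as incompatible with cure.

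It is of the lowest severity. Clinical cure is secondary and descriptive, the SAP plans only listings for it, and no test or decision depends on the early proportion. The number affected is most likely zero. The shift of up to 4.0 or 6.7 points rests on the assumption of one affected patient in a group of the planned size. It should not be read as evidence that the early success rate will be materially inflated, since the documents give no frequency for such drug use.

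**What to change.** Leave the current 48-72 hour antibacterial item as it is, so that drugs given for the ABSSSI still count as early failure. Add one item to the same list, using the Day 7 wording, "Initiation of non-study antibacterial drugs for treatment of other infection unless antibiotic lacks efficacy in the treatment of ABSSSI", limited to drugs started after the start of oritavancin and before the 48-72 hour evaluation. Keep the Day 7 phrase otherwise unaltered, so that the two lists apply the same test. The Day 7 list needs no change.

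The cost is one line. It requires no new visit, test or restriction on care, and concomitant medications are already captured. The early success figure may be slightly less favourable. Day 7 results would not move, because any patient newly failed at 48-72 hours under this line already fails at Day 7 under the existing item.

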# Investigator assessment of clinical cure:

At Day 7: Complete or nearly complete resolution of baseline signs and symptoms of the primary infection such that no further treatment with antibiotics is needed

A patient cannot be classified as clinical cure if:

- Patient did not fulfill criteria for clinical cure above
- Investigator assignment of failure any time prior to Day 7
- Patient dies (all-cause mortality) from the start of administration of oritavancin
- Incision and drainage after 48 hours of treatment that was unplanned prior to enrollment, with the exception of cellulitis where there is a conversion into an abscess or when an extension of the original incision is indicated
- Initiation of non-study antibacterial drugs for treatment of other infection unless antibiotic lacks efficacy in the treatment of ABSSSI
- Subjects who otherwise do not meet the definition of clinical cure (e.g., lost to follow-up; oritavancin discontinued secondary to adverse reaction)

A patient who is not classified as clinical cure will be classified as failure.

#### 8. ADVERSE EVENTS

# 8.1. **DEFINITIONS**

#### 8.1.1. Adverse Event

An adverse event (AE) is defined as any untoward medical occurrence in a subject or clinical investigation subject administered a medicinal product and which does not necessarily have a causal relationship with this treatment. An AE can therefore be any unfavorable and unintended sign (including an abnormal laboratory finding), symptom or disease temporally associated with the use of a medicinal product, whether or not considered related to the medicinal product.

Planned hospital admissions and/or surgical operations for an illness or disease that existed before the drug was given or the subject was enrolled in a clinical study are not to be considered AEs.

Subjects experiencing adverse events should be followed clinically until their health has returned to baseline status or until all parameters have returned to normal or have otherwise been explained. It is expected that the investigator will provide or arrange appropriate supportive care for the subject if necessary.

# **8.1.1.1. AE** Severity

The severity of an AE will be assessed by the investigator. The investigator should ensure that any subject experiencing an AE receives appropriate medical support until the event resolves.

AEs will be graded on a 3-point scale and reported as indicated on the case report form. The intensity of an AE is defined as follows:

- 1 = Mild: Discomfort noticed, but no disruption to daily activity.
- 2 = Moderate: Discomfort sufficient to reduce or affect normal daily activity.
- 3 = Severe: Inability to work or perform normal daily activity.

# 8.1.1.2. Study Drug Causality

The relationship of an AE to study treatment will be assessed with consideration to the following criteria:

- Temporal relationship to the initiation of study medication
- Response of the event to withdrawal of study medication
- AE profile of concomitant therapies
- Clinical circumstances during which the AE occurred

• Subject's clinical condition and medical history

Categorization of causality will be designated by the investigator as stated below:

- 1. **Unlikely related -** Lack of reasonable possibility of a causal relationship causal relationship between the event and the IMP. This means that there are little to no facts (evidence) or arguments to suggest a causal relationship.
- 2. **Reasonable Possibility** Reasonable possibility of a causal relationship causal relationship between the event and the IMP. This means that there are facts (evidence) or arguments to suggest a causal relationship.

#### 8.1.2. Serious Adverse Event

A serious adverse event (SAE) is any untoward medical occurrence that at any dose:

- Results in death,
- Is life-threatening, i.e., the subject was, in the opinion of the investigator, at immediate risk of death from the event as it occurred (it does not include an event that, had it occurred in a more severe form, might have caused death),
- Results in a significant, persistent or permanent change, impairment, damage or disruption in the subject's body function/structure, physical activities and/or quality of life,
- Requires in-patient hospitalization or prolongs hospitalization,
- Is a congenital anomaly/birth defect, or
- Is another medically significant event that, based upon appropriate medical judgment, may jeopardize the subject and may require medical or surgical intervention to prevent one of the outcomes listed above (e.g., allergic bronchospasm requiring intensive treatment in an emergency department or home, blood dyscrasias or convulsions that do not result in hospitalization, or the development of drug dependency or drug abuse).

A distinction should be drawn between serious and severe AEs. Severity is an estimate or measure of the intensity of an AE, while the criteria for serious AEs are indications of adverse subject outcomes for regulatory reporting purposes. A severe AE need not necessarily be considered serious and a serious AE need not be considered severe. For example, nausea that persists for several hours may be considered severe nausea, but not an SAE. On the other hand, a myocardial infarction (MI) that may be considered minor could also be an SAE if it prolonged hospitalization.

When death occurs with an SAE, the cause of death must be reported as an SAE. "Fatal" will be reported as the outcome for these events.

#### **8.1.3.** Medication Errors

Medication error refers to any unintended error in the dosing and administration of the study product as per instructions in the protocol. Medication Errors generally fall into 4 categories as follows:

- 1. wrong medication
- 2. wrong dose (including dosing regimen, strength, form, concentration, amount);
- 3. wrong route of administration;
- 4. wrong patient (i.e. not administered to the intended patient)

Medication Errors include occurrences of overdose and underdose of the study product(s), and misuse.

**Overdose:** Administration of a quantity of the study product given per administration or per day which is above the maximum recommended dose according to the reference safety information or protocol for the investigational product or comparator as applicable. This also takes into account cumulative effects due to overdose.

**Underdose:** Administration of a quantity of the study product given per administration or per day which is under the minimum recommended dose according to the reference safety information or protocol for the investigational product.

Misuse: Intentional and inappropriate use of a medicinal product not in accordance with the prescribed or authorised dose, route of administration, and/or the indication(s) or not within the legal status of its supply (e.g. without prescription for medicinal products subject to medical prescription).

# **8.1.4.** Reporting Medication Errors

Medication errors with or without an associated AE need to be recorded as medication errors in the eCRF as described in Section 8.2.

Medication errors with an associated SAE need to be recorded as medication errors in the eCRF and reported to MDCO Global Pharmacovigilance as described in Section 8.3.

A mis-dosing protocol deviation (refer to Section 12.3) would need to be reported as a medication error if it was an "unintended error" as defined in Section 8.1.3.

# **8.1.5.** Reporting Events of Pregnancy

Occurrences of pregnancy in a study subject or study subject's partner, including pregnancies detected anytime from administration of oritavancin until 60 days after administration of oritavancin, must be reported within 24 hours using the Pregnancy Reporting form. In cases where a pregnancy occurs with a Serious Adverse Event, the Serious Adverse Event reporting form should be used to report the SAE and the Pregnancy Reporting form should be used to report the pregnancy. Any spontaneous abortion must be captured as a SAE. When a pregnancy occurs without any intercurrent SAE, the Pregnancy Reporting form may be submitted alone. Follow-up through pregnancy outcome is required if a pregnancy is detected during this study.

The Medicines Company or its designee will contact the investigator, if necessary, to clarify any of the pregnancy information. The investigator will provide follow-up information to MDCO or its designee as soon as it becomes available. Additionally, if required by local regulations or procedures, the investigator will report pregnancies to the Institutional Review Board (IRB)/Ethics Committee (EC) and/or national or local regulatory authorities.

#### 8.2. PROCEDURE FOR NON-SERIOUS ADVERSE EVENT RECORDING

All non-serious AEs that occur during the designated study period (from signing the inform consent to 14 days following initial oritavancin administration) must be assessed and recorded on the source documents and eCRF, regardless of causal relationship to the study drug.

### 8.3. PROCEDURE FOR SERIOUS ADVERSE EVENT REPORTING

All SAEs that occur during the designated study period (from signing the informed consent to 14 days following initial warfarin administration) must be reported to The Medicines Company (MDCO) within 24 hours of awareness of the event using the provided study specific SAE Report Form. The completion and processing of the SAE Report Form (paper) should follow the instructions provided in the SAE Report Form completion guidelines. In addition to completing the SAE Report Form, each SAE must be entered on the appropriate page of the eCRF.

The investigator must assess the causality for each SAE.

MDCO will contact the investigator, if necessary, to clarify any of the event information. The investigator should provide any follow-up information for the event to MDCO as soon as it becomes available.

If the investigator is notified of an SAE that occurs during post-study period, that he or she wishes to report to the Sponsor (e.g., an event suspected to be causally related to study drug), the event should be reported through the process described above.

Where appropriate, if required by local regulations or procedures, the investigator should report these events to the Institutional Review Board (IRB)/Ethics Committee (EC) and/or national regulatory authority.

